9.6 Steering Committee

The Steering Committee will be the primary governing body of the study and provides its scientific leadership. It will have responsibility for the overall study design, policy decisions and operations of the OAI. Voting members of the Steering Committee will include 2 representatives (the principal investigators and coinvestigators) from each of the clinical centers and the coordinating center, the NIAMS project officer and a representative from NIA, and 2 representatives from the pharmaceutical sponsors. Nonvoting participants will include an FDA-appointed representative to serves as a liaison between FDA and the OAI, outside consultants as needed, and others as decided by the Steering Committee. Major scientific and protocol decisions will be determined by majority of the voting members of the Steering Committee. The Steering Committees of investigators and staff as needed throughout the study. These will include Imaging, Measurements, Recruitment and Retention, Quality Assurance, and Ancillary Studies and Publications. Subcommittees will be chaired by a member of the Steering Committee, who will report its activities to the Steering Committee.

9.6.1 Protocol amendments and changes in study procedures

Changes in the protocol and procedures will be adopted by a majority vote of the Steering Committee. A record of changes in study procedures and conduct will be maintained by the coordinating center. Changes that alter the written study protocol will be summarized in an appendix to the current version of the protocol (Appendix K).

9.7 Biospecimen Resource Allocation Committee

The NIH will select, with recommendations from the Steering Committee, a Biospecimen Resource Allocation Committee (BRAC) that will oversee the allocation and distribution of biological specimens generated from the OA Initiative. The BRAC will be made up of individuals not directly involved in the OA Initiative or cartilage-related research and without conflict of interest. Membership on this committee will rotate multi-year terms. Meetings of the BRAC will be widely advertised. The BRAC will review applications to use the biological specimens. The format of the application and criteria for the use of repository biological specimens will be developed by the BRAC with advice from the Steering Committee and made available to potential users.

9.8 Observational Study Monitoring Board

The NIH will establish and appoint members of an Observational Study Monitoring Board (OSMB) to monitor regularly the data from the observational study, review and assess the study performance, and to make recommendations, as appropriate, to the NIH with respect to 1) the performance of individual centers; 2) issues related to participant safety and informed consent, including notification of and referral for abnormal findings; 3) adequacy of study progress in terms of recruitment, quality control, data analysis, and publications; 4) issues pertaining to participant burden; 5) impact of proposed ancillary studies and sub-studies on participant burden and overall achievement of the main study goals; and 6) overall scientific directions of the study. The NIH will be responsible for organization

and scheduling of these meetings. The coordinating center will provide to the OSMB materials needed to carry out the evaluations described above.

10.0 ANCILLARY STUDIES

An ancillary study will be a study that requires access to OAI participants, whether from a single clinical center or from the entire cohort, to collect measurements or data that are not part of the core protocol or routine OAI database or that enrolls additional participants needed to address a specific research question. The Steering Committee and/or the Ancillary Studies subcommittee will review and approve proposals and protocols for ancillary studies. Ancillary studies must be approved by the institutional review boards of the participating centers and may require separate consent.

The following will not be considered ancillary studies for the purposes of these guidelines:

- studies that generate new data that are not part of the routine OAI database from existing measurements (such as measurements from joint images);
- studies that generate new data from stored core biospecimens (Such studies will be reviewed and require approval by the Biospecimen Resource Allocation Committee.);
- substudies funded by the OAI, such as modifications or additions to the existing contract.

Ancillary study guidelines will be developed by the Steering Committee (Appendix L).



Appendix A. Original Study Enrollment Goals for Progression and Incidence Subcohorts, by Age and Gender

The OAI plans to enroll 5,000 women and men ages 45 to 79, 800 in the Progression subcohort, 4,000 in the Incidence subcohort, and 200 in the reference ("nonexposed") control group. Sample sizes in the Progression and Incidence subcohorts are expected to provide adequate numbers of knees with worsening and incident OA-related structural and clinical changes to achieve the primary aims of the study.

Age stratum	Women	Men	Total N (%)
Age 45-49	80	80	160 (20%)
Age 50-59	104	104	208 (26%)
Age 60-69	112	112	224 (28%)
Age 70-79	104	104	208 (26%)
Age 45-79	400	400	800 (100%)

Table 1. Progression subcohort: number of enrollees at baseline

The target number of enrollees by age-stratum and gender is shown in Tables 1 and 2. The target number of enrollees will be equal by gender in all age strata of the cohorts. In the Progression subcohort (Table 1), enrollment goals will be similar for each of four age-strata. For the reference control group, goals will also be similar by age strata. In the Incidence subcohort (Table 2), the number of enrollees per age stratum will yield roughly equal numbers of cases of incident knee OA by gender and roughly equal numbers of incident cases by 10-year age strata.

Age stratum	Women	Men	Total N (%)
Age 45-49	140	140	280 (7%)
Age 50-59	472	472	944 (24%)
Age 60-69	780	780	1560 (39%)
Age 70-79	608	608	1216 (30%)
Age 45-79	2000	2000	4000 (100%)

Table 2. Incidence subcohort: number of enrollees at baseline

Appendix B. Modeling OAI Incidence Subcohort Enrichment Using Risk Factors

[name], Boston University [name], UCSF Updated 4/15/03

I. SUMMARY

We estimated the effect of using risk factors to enrich the Incidence subcohort for the endpoint of incident symptomatic knee OA. For this we pooled subjects from both the original Framingham Cohort¹, most of whom were over age 70, and the second-generation Framingham Offspring Cohort², most of whom were under age 70, to derive the level of risk associated with various combinations of most of the risk factors listed in Section I.3. Men and women aged 45 to 79 years old are included in these analyses. Symptomatic knee OA is defined as the presence of both knee pain on most days of the month and Kellgren and Lawrence grade of 2 or more on the AP radiograph in the same knee. All data are cross-sectional, and prevalence rather than incidence was analyzed.

The Framingham study subjects were separated into 6 strata by sex and age. All analyses were performed stratified by these 6 groups:

- 1. Men ages 45-49
- 2. Men ages 50-69
- 3. Men ages 70-79
- 4. Women ages 45-49
- 5. Women ages 50-69
- 6. Women ages 70-79

Within each stratum, "high risk" subgroups were defined using risk factors. The prevalence ratios for the high risk subgroups were determined by dividing the prevalence of symptomatic knee OA among high risk subjects in a sex and age stratum back to the prevalence in all subjects in that stratum. The resulting prevalence ratios were used as multipliers applied to the gender and age-specific incidence of clinical symptomatic knee OA from the Fallon Community Health Planⁱ. ³

The following items were analyzed as risk factors for symptomatic knee osteoarthritis:

• Pain in knee on most days of the preceding month

¹ The estimates for incident symptomatic knee OA from Framingham (1) are consistent with the rates from the Fallon study. In the Framingham study, subjects were mostly age 70 or older and were followed for eight years. For women, the per person incidence of symptomatic knee OA was 1% per year; for radiographic knee OA it was 2%/year and for progressive radiographic disease, it was 4%/year. Rates are slightly lower for men in Framingham. High BMI increased the risk of incident and progressive OA in women, but not among all men.

- Previous knee injury
- Previous knee operation
- Weight
- Presence of Heberden's nodes in the DIP joints of both hands (this is only available currently in members of the original Framingham cohort, who are mainly in strata 3 and 6).

Some risk factors that will be used in OAI screening could not be evaluated in this fashion due to lack of data in the Framingham cohorts, including total knee replacement in a parent or sibling and current frequent knee bending.

To help determine which weight cut-points were most useful, we considered three stratum-specific cutpoints in conjunction with the other risk factors: top 15^{th} percentile of weight, top 30^{th} percentile of weight, and top 50^{th} percentile of weight. Similar results were found using BMI percentile cut-points instead of weight.

We also considered an alternative definition for Heberden's nodes, which was bilateral nodes plus total number of nodes above the median for the stratum. This had a small effect on both the percent at risk and the prevalence ratio, and was not considered further.

The following definitions of "high risk" were selected based on a reasonable balance between effectiveness in enriching the cohort (high prevalence ratio) and feasibility of recruitment (high percent who would be classified as "high risk").

Age 45-49 high riskⁱⁱ

- Subject has knee pain and one or more non-pain risk factor (using 30th percentile weight cut-point) Age 50-69 high riskⁱⁱⁱ
- Subject has knee pain or 2 or more non-pain risk factors (using 30th percentile weight cut-point) Age 70-79 high risk
- Subject has knee pain or 1 or more non-pain risk factor (using 15th percentile weight cut-point)

ⁱⁱ As it was anticipated that men and women aged 45 to 49 years will need additional risk factors to make their inclusion 'power-neutral', we consider a different risk factor threshold for these strata. Due to the small numbers of cases of symptomatic knee OA in this group, more restrictive thresholds (i.e. requiring pain plus 2 or more risk factors) lead to having no cases in the at risk group

ⁱⁱⁱ For the 50-69 and 70-79 age groups, two alternative definitions of high risk were evaluated, 1 or more risk factors and 2 or more risk factors.

					% of	Prevalence
	N of	Knee pain	X-ray knee	Sx knee	stratum	ratio in
Stratum	subjects	(%)	OA (%)	OA (%)	in high risk	high risk
1. Men, 45-49	130	17.7	8.5	3.1%	7.7%	9.7
2. Men, 50-69	614	19.1	20.0	5.5%	26.1%	3.9
3. Men, 70-79	382	12.5	29.8	6.3%	47.6%	2.1
4. Women, 45-49	138	26.1	5.1	$0.7\%^{3}$	9.4%	ND [*]
5. Women, 50-69	729	24.1	19.1	6.9%	31.4%	3.2
6. Women, 70-79	553	20.5	38.2	11.8%	60.9%	1.6

Table 1. Results of modeling incidence subcohort enrichment for above			
definitions of "high risk"			

There is only 1 case of symptomatic OA in this group, and it lies in the upper 15% of weight.

For the 50-69 year age strata, using the 50% instead of the 30% weight cut-point would slightly increase the proportion of the stratum at high risk but also decrease the prevalence ratio. For men, these estimates were 29.2% of the age group at high risk and with a prevalence ratio of 3.5, while for women the results were 36.5% and 2.7, respectively.

for each genuer and age group							
	Base annual	Adjusted	Adjusted				
	risk	annual	annual				
Gender and age groups	of clinical	risk or clinical	risk of Sx				
	knee OA [*]	knee OA**	knee OA***				
Men, 45-49	0.15	0.98	1.07				
Men, 50-59	0.25	0.98	1.07				
Men, 60-69	0.49	1.91	2.10				
Men, 70-79	0.84	1.76 ^{&}	1.94				
Women, 45-49	0.15	0.91	1.01				
Women, 50-59	0.28	0.90	0.99				
Women, 60-69	0.66	2.11	2.32				
Women, 70-79	1.08	1.73	1.90				

 Table 2. Rates for symptomatic knee OA used in endpoint calculations, for each gender and age group

* Annual incidence of clinical knee OA per 100 p-yrs from Oliveria, et al 1995 ³

** Adjusted incidence per 100 p-yrs equals the base annual risk times the prevalence ratios from Table 1. For ages 45-49, we used a multiplier that made the adjusted incidence rate in this group equal to the adjusted incidence rate in the 50-59 age group, 6.5 for men and 6.1 for women. Within each gender, the multiplier estimated for the 50-69 stratum was used with the 50-59 and 60-69 year old incidence from Fallon.

**** Annual incidence of symptomatic knee OA per 100 p-yrs assumed to be 10% higher than clinical knee OA.

[&] Because the risk multiplier is so much higher in the 60-69 compared to the 70-79 year age group, the adjusted annual risk ends up being a little higher in the younger subjects.

We multiplied the prevalence ratios from Table 1 times the annual risk of clinical knee OA observed in the Fallon HMO population to obtain an estimate of the annual risk of clinical knee in the high risk groups (adjusted annual risk) (Table 2). Because of the small numbers of men in the 45-49 year age group in the sample, estimates of prevalence ratios in this group may be unstable. Further, there was only one woman with symptomatic knee OA in this age group. Therefore, we did not use empirically

OAI Protocol Appendix B

derived prevalence ratios for this age group. Instead, we calculated the multiplier that would be needed to make the adjusted annual risk in the 45-49 year olds equal to the adjusted annual risk in the 50-69 year olds. For men this was 6.5 and for women this was 6.1, which is less than the prevalence ratio actually observed for men this age.

For the annual incidence of symptomatic knee OA in each age and gender group (Table 2), we assumed (based on data from Framingham) that the incidence of symptomatic knee OA (defined as the first cooccurrence of knee pain on most days of a month and Kellgren-Lawrence grade 2 or higher radiographic knee OA) is 10% greater than the incidence of clinical knee OA. The adjusted annual risk per 100 personyears for symptomatic knee OA in Table 2 and the age and gender specific recruitment goals for the Incidence subcohort (Appendix A) were used to estimate the number of endpoints expected in Table 3.

	Subjects with	Knees with
Gender/	Incident Sx OA	Incident Sx OA
Age stratum	N (%)	
Men age 45-69	73 (32%)	121 (32%)
Men age 70-79	37 (17%)	62 (17%)
Men age 45-79	110 (49%)	183 (49%)
Women age 45-69	76 (34%)	127 (34%)
Women age 70-79	37 (17%)	61 (17%)
Women age 45-79	113 (51%)	188 (51%)
All subjects	223 (100%)	371 (100%)

Table 3. Expected number of cases of incident symptomatic
knee OA in the Incidence subcohort

The number of incident knees is expected to be about 60-70% greater than the number of incident case subjects since most subjects will have two knees at risk.¹ (and unpublished data from Framingham)

Limitations of the enrichment modeling

There are several limitations and uncertainties of these analyses. First, we were not able to model incidence directly as the existing data sets contain only a small number of cases of incident symptomatic knee OA. Risk multipliers drawn from cross-sectional analyses of risk factors and symptomatic OA may not apply to risk factors for true incidence. It is also uncertain whether analysis using incident radiographic OA, a more common endpoint that has been used in several existing cohort studies, would provide more valid inference since it is not known whether risk factors for incident radiographic OA differ from those for symptomatic OA. In addition, there were no data available for modeling on incidence of symptomatic knee OA as specifically defined in the present analyses, which is the first co-occurrence of knee pain on most days of a month and Kellgren and Lawrence grade 2 or greater radiographic OA.

Consistency of results with previous studies of risk factors for incident knee OA

However, our results are concordant with the small number of studies that have directly assessed risk factors for incident radiographic OA. In a cohort of 2,101 men and women ages 55 and older living in Bristol, England, high BMI, knee pain at baseline, Heberden's nodes, previous knee injury and regular sports participation each independently increased the risk of incident radiographic OA⁴. In a cohort of over 1000 women ages 45 to 60 residing in Chingford, England, those with incident knee OA were

OAI Protocol Appendix B

heavier, had more hand OA and more often had knee symptoms than those who did not develop OA⁵. In analyses of incident radiographic knee OA in the original (older) Framingham cohort, higher BMIs and high levels of physical activity increased the risk of incident knee OA in both genders⁶. In addition, there were nonsignificant trends for an increased risk in Framingham men with hand OA and previous knee injury and for women with a knee injury during follow-up. Women in Framingham had a 1.8 to 2.0 fold higher risk than men for both incident radiographic and incident symptomatic knee OA in these older Framingham subjects¹. This last finding supports the higher base rates for incident clinical knee OA that we are using for women, based on the Fallon Health Plan data³. Finally, in the only study of risk factors for incident clinical knee OA, heavier women in the Fallon Health Plan had a greatly increased risk of new knee OA⁷.

II. DETAILED TABLES OF RESULTS

1. Number of subjects and prevalence of Sx knee OA for sex and age strata

Weight cut-points were based on percentile distributions in the Framingham cohort. Weight values for percentile cut-points used in OAI are taken from the weight distributions of the 2001 National Health Interview Survey, which are higher than those corresponding weights in Framingham.

Stratum	Number of	Subjects with	Knee OA
	Subjects	Knee OA	Prevalence (%)
1. Men, 45-49	130	4	3.1
2. Men, 50-69	614	34	5.5
3. Men, 70-79	382	24	6.3
4. Women, 45-49	138	1	0.7
5. Women, 50-69	729	50	6.9
6. Women, 70-79	553	65	11.8

2. Weight Cutoffs by Strata

Table entry is weight in pounds

Stratum	Upper 50% Cutoff	Upper 30%Cutoff	Upper 15% Cutoff
1. Men, 45-49	184	202	222
2. Men, 50-69	185	199	213
3. Men, 70-79	167	180	193
4. Women, 45-49	146	169	191
5. Women, 50-69	145	159	173
6. Women, 70-79	139	151	167

3. Results for men 45-49 years of age (Stratum 1)

Tables show the prevalence ratio (PR) vs. prevalence in all subjects in that stratum for "at risk" defined by knee pain and 1+ risk factors

3A. Endpoint is symptomatic OA.

At risk group for		PR: At Risk	
different weight cut-	PPV: % with	(pain and 1+	
points	Sx knee OA	risk factors)	% (n) at Risk
A. 15% wt	28.8	9.28	5.4 (7)
B. 30% wt	30.1	9.74	7.7 (10)
C. 50% wt	23.3	7.49	10.0 (13)

3B. Endpoint is X-ray OA (Because of the small numbers of cases of Sx knee OA in this age group, we also examined the effect of risk stratification on the prevalence of X-ray OA)

At risk group for		PR: At Risk	
different weight cut-	PPV: % with	(pain and 1+	
points	Radiographic	risk factors)	% (n) at Risk
	knee OA		
A. 15% wt	28.6	3.38	5.4 (7)
B. 30% wt	30.0	3.55	7.7 (10)
C. 50% wt	23.1	2.73	10.0 (13)

4. Results for men 50-69 years of age (Stratum 2)

Tables show the prevalence ratio (PR) vs. prevalence in all subjects in that stratum for:

4A. "at risk" defined by knee pain or 2+ risk factors

At risk group for		PR: At Risk	
different weight cut-	PPV: % with	(pain or 2+	
points	Sx knee OA	risk factors)	% (n) at Risk
A. 15% wt	23.1	4.20	23.9 (147)
B. 30% wt	21.2	3.85	26.1 (160)
C. 50% wt	19.0	3.45	29.2 (179)

4B. "at risk" defined by knee pain or 1+ risk factors

	At risk group for		PR: At Risk	
	different weight cut- points	PPV: % with Sx knee OA	(pain or 2+ risk factors)	% (n) at Risk
1	A. 15% wt	12.1	2.20	45.8 (281)
]	B. 30% wt	9.8	1.78	56.4 (346)
(C. 50% wt	8.1	1.47	68.6 (421)

5. Results for men 70-79 years of age (Stratum 3)

Tables show the prevalence ratio (PR) vs. prevalence in all subjects in that stratum for:

5A. "at risk" defined by pain or 2+ risk factors

At risk group for		PR: At Risk	
different weight cut-	PPV: % with	(pain or 2+	
points	Sx knee OA	risk factors)	% (n) at Risk
A. 15% wt	28.8	4.57	13.6 (52)
B. 30% wt	26.4	4.19	17.8 (68)
C. 50% wt	23.0	3.65	23.8 (91)

5B. "at risk" defined by pain or 1+ risk factors

At risk group for different weight cut-	PPV: % with	PR: At Risk (pain or 2+	
points	Sx knee OA	risk factors)	% (n) at Risk
A. 15% wt	13.2	2.10	47.6 (182)
B. 30% wt	11.1	1.76	56.5 (216)
C. 50% wt	9.2	1.46	68.3 (261)

6. Results for women 45-49 years of age (Stratum 4)

Tables show the prevalence ratio (PR) vs. prevalence in all subjects in that stratum for "at risk" defined by pain and 1+ risk factors

6A. Endpoint is symptomatic OA.

At risk group for		PR: At Risk	
different weight cut-	PPV: % with	(pain and 1+	
points	Sx knee OA	risk factors)	% (n) at Risk
A. 15% wt	12.50	17.36	5.8 (8)
B. 30% wt	7.69	10.68	9.4 (13)
C. 50% wt	4.55	6.32	15.9 (22)

*Note that there is only 1 case in this group, and it lies in the upper 15% of weight.

6B. Endpoint is X-ray OA (Because of the small numbers of cases of Sx knee OA in this age group, we also examined the effect of risk stratification on the prevalence of X-ray OA)

At risk group for		PR: At Risk	
different weight cut-	PPV: % with	(pain and 1+	
points	Sx knee OA	risk factors)	% (n) at Risk
A. 15% wt	12.50	2.47	5.8 (8)
B. 30% wt	7.69	1.52	9.4 (13)
C. 50% wt	4.55	0.90	15.9 (22)

7. Results for women 50-69 years of age (Stratum 5)

Tables show the prevalence ratio (PR) vs. prevalence in all subjects in that stratum for:

At risk group for different weight cut-	PPV: % with	PR: At Risk (pain or 2+	
points	Sx knee OA	risk factors)	% (n) at Risk
A. 15% wt	24.2	3.51	28.4 (207)
B. 30% wt	21.8	3.16	31.4 (229)
C. 50% wt	18.8	2.72	36.5 (266)

7A. "at risk" defined by pain or 2+ risk factors

7B. "at risk" defined by pain or 1+ risk factors

At risk group for different weight cut-	PPV: % with	PR: At Risk (pain or 2+	
points	Sx knee OA	risk factors)	% (n) at Risk
A. 15% wt	12.6	1.83	54.3 (396)
B. 30% wt	11.0	1.59	62.3 (434)
C. 50% wt	9.4	1.36	73.0 (532)

8. Results for women 70-79 years of age (Stratum 6)

Tables show the prevalence ratio (PR) vs. prevalence in all subjects in that stratum for:

8A. "at risk" defined by pain or 2+ risk factors

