4.2.2.3 Incidence subcohort

Participants in the Incidence subcohort will not have symptomatic knee OA, as defined above, in either knee at baseline. However, they will have characteristics that place them at increased risk for developing symptomatic knee OA during the study. Incident symptomatic knee OA will be defined as

V 1.1 6.21.06

the first occurrence during the study of frequent knee symptoms and definite tibiofemoral osteophytes in the same knee.

The eligibility criteria used to define "increased risk" represent established or putative risk factors for incident knee OA that can be assessed over the telephone. Analyses of existing data sets focusing on symptomatic knee OA as the outcome identified combinations of characteristics in each age and gender subgroup that will sufficiently enrich the cohort for risk of incident symptomatic knee OA. The details of the modeling analyses using various definitions of "increased risk" are contained in Appendix B.

The following age-specific eligibility criteria will allow a reasonable balance between effectiveness in enriching each stratum with incident events and the feasibility of recruitment, i.e. a high percent of age-eligible persons screened will be classified as "high risk." and therefore eligible:

- For those age 45-49, eligible participants will have frequent knee symptoms (defined above), or frequent use of medications for treatment of knee symptoms (defined below), or infrequent knee symptoms (defined below); AND will have one or more other eligibility risk factor (defined below).
- For those age 50-69, eligible participants will have any of the following: frequent knee symptoms, or frequent use of medications for treatment of knee symptoms, or be overweight, or have two or more other eligibility risk factors.
- For those age 70-79, eligible participants will have any of the following: frequent knee symptoms, or frequent use of medications for treatment of knee symptoms, or one or more other eligibility risk factor.

The specific eligibility risk factor criteria for the Incidence subcohort will be:

Knee symptoms in a native knee in the past 12 months. Three definitions of knee symptoms during the past 12 months will be used as risk factors for eligibility purposes:

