The overall incidence of symptomatic knee OA expected among subjects selected for the OAI Incidence subcohort is 1.8/100 person-years in men and women combined. Adjusted age-specific risks range from about 1.0/100 p-y at age 45-49 to about 2.0/100 p-y in those age 60 and over and are similar by gender. This compares with an observed range in age-specific risks of about 0.2/100 p-y to

0.8/100 p-y in the general population in the same age strata.(35) Cumulative incidence after 4 years is expected to be about 5.5%.

It is likely that these are conservative estimates. The increased risk in the overweight groups derived from the cohort enrichment modeling suggest a smaller effect of weight than is seen in the existing incidence studies. In the Fallon Health Plan, women (mean age 60) who weighed 175 lbs or more had a 5 to 6 fold increased risk of incident clinical knee OA compared to those who weighed less.(138) In the Bristol cohort, men and women in the highest third of BMI (≥ 25.4 kg/m2) had at least a 9-fold higher risk of developing knee OA than those in the lower third.(15) This compares to a risk ratio of 2.0 for prevalent symptomatic knee OA in the upper third of weight in Framingham women and 1.6 for the upper third of weight in men (Appendix B).

Most participants in this subcohort will have two knees at risk for incident disease, and consistent with this the number of knees with incident symptomatic OA (Table 8.1) is projected to be greater than the number of incident case subjects.(20) (and unpublished data) In addition, contralateral knees in the Progression subcohort that are free of prevalent disease at baseline have a high risk of developing OA(139) and may be pooled with cases from the Incidence subcohort for some analyses.

	Subjects with	Knees with
Gender/	Incident Sx OA	Incident Sx OA
Age stratum	Ν	N (%)
Men age 45-69	73	121 (32%)
Men age 70-79	37	62 (17%)
Men age 45-79	110	183 (49%)
Women age 45-69	76	127 (34%)
Women age 70-79	37	61 (17%)
Women age 45-79	113	188 (51%)
All subjects	223	371 (100%)

Table 8.1 Expected number of cases of incident symptomatic knee OA based on enrollment goals in the Incidence subcohort

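### The Appendix B enrichment multipliers at ages 50-79 are circular, because knee pain is in both the risk definition and the outcome, so the 223 expected incident cases have no demonstrated conservative margin

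*Protocol*

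**What the plan says.** Appendix B models enrichment of the Incidence subcohort from pooled Framingham data. The outcome is given as: "Symptomatic knee OA is defined as the presence of both knee pain on most days of the month and Kellgren and Lawrence grade of 2". That grade is a minimum, and both findings must be in one knee. The first risk factor listed is "Pain in knee on most days of the preceding month". A person aged 50-69 is high risk with knee pain or at least two non-pain factors. A person aged 70-79 is high risk with knee pain "or 1 or more non-pain risk factor (using 15th percentile weight cut-point").

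The appendix is open that "All data are cross-sectional, and prevalence rather than incidence was analyzed". The ratio of high-risk prevalence to whole-stratum prevalence is then carried over to incidence: "The resulting prevalence ratios were used as multipliers applied to the gender and age-specific incidence of clinical symptomatic knee OA". For ages 45-49 the observed ratios are set aside, and multipliers of 6.5 (men) and 6.1 (women) are imposed so that the rate matches that at 50-59.

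Section 8.2.4 derives 223 subjects and 371 knees from these rates (Table 8.1), 265 effective independent knees, and the detectable relative risks in Table 8.2. It comments: "It is likely that these are conservative estimates". Section 8.2.4.1 again describes base rates and enrichment as conservative, and offers this as a partial offset to low enrolment.

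Section 4.2.2.3 now admits people aged 50-69 with frequent symptoms "or frequent use of medications for treatment of knee symptoms, or be overweight, or have two or more other eligibility risk factors". Overweight alone is therefore sufficient, which the Appendix B model did not include.

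**The concern.** A prevalence ratio can stand in for a risk multiplier only if it reflects an association between the factors and the disease. Here predictor and outcome share a component. A person cannot be a case without the pain that already places them in the high-risk group. The captured share of cases is then 100% whatever the real strength of the risk factors, and the ratio is fixed by the size of the high-risk group alone. Its numerator consists entirely of people with prevalent symptomatic OA, whom the Incidence subcohort excludes.

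The argument for conservatism in section 8.2.4 is that the modelled weight effect is smaller than in incidence studies. That cannot supply a margin in this calculation: with all cases already captured, a stronger weight effect would leave the ratio unchanged.

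At stake are the expected 223 cases, the 265 effective knees, Table 8.2, and the roughly 300 case knees that section 8.2.4 calls a conservative basis for Table 8.3.

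**Working it through.** **1. Reproducing 223.** Inputs: annual rates q from Appendix B Table 2, goals N from Appendix A (per sex 140, 472, 780, 608), and dropout of 10% then 7% a year (section 8.2.4), giving retention R of 0.900, 0.837, 0.778 and 0.724. Cases per cell = N × Σ R(t) × q × (1−q)^(t−1).

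- Men: 4.8 + 16.1 + 51.5 + 37.2 = 109.6 (stated 110)
- Women: 4.5 + 14.9 + 56.7 + 36.4, total 112.6 before rounding the cells (stated 113)
- Total 222 (stated 223). Also 371/1.4 = 265.

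**2. Circularity.** Counts are from the Appendix B detailed tables used for the multipliers.

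| Stratum | N | Cases | n high risk | PPV × n | N/n | Stated ratio |
|---|---|---|---|---|---|---|
| Men 50-69 | 614 | 34 | 160 | 33.9 | 3.84 | 3.85 |
| Men 70-79 | 382 | 24 | 182 | 24.0 | 2.10 | 2.10 |
| Women 50-69 | 729 | 50 | 229 | 49.9 | 3.18 | 3.16 |
| Women 70-79 | 553 | 65 | 337 | 65.0 | 1.64 | 1.64 |

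All cases are captured in all four strata, and each ratio equals N/n up to rounding. The 45-49 multipliers are not such ratios, but they are set to match the 50-59 rate and so inherit the problem.

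**3. What a real multiplier would look like.** Let high-risk people have r times the incidence of others, and let f be the high-risk fraction. The multiplier relative to the whole stratum is m = r/(1 + f(r−1)), which tends to 1/f as r grows. Because prevalent cases are excluded from the subcohort, they are removed from both groups: f = (n − cases)/(N − cases).

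- Men 50-69: 126/580 = 0.217, maximum m 4.60
- Men 70-79: 158/358 = 0.441, maximum m 2.27
- Women 50-69: 179/679 = 0.264, maximum m 3.79
- Women 70-79: 272/488 = 0.557, maximum m 1.79

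Example, men 60-69 with r = 3: m = 3/(1 + 0.217 × 2) = 2.09. The annual rate is 0.49 × 1.1 × 2.09 = 1.13 per 100, against 2.10 in the plan.

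**4. Expected cases at goal enrolment.** Base rates and the 1.1 factor are as stated, and the 45-49 rate is kept equal to the 50-59 rate. Knees = cases × 371/223; effective knees = knees/1.4. Detectable relative risks use the plan's own conversion in the footnote to Table 8.5: stated value raised to the power √(223/cases).

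| Assumption | Cases | Knees | Effective knees | RR at 50% exposure (stated 1.43) | RR at 10% exposure (stated 1.70) |
|---|---|---|---|---|---|
| No enrichment | 84 | 140 | 100 | 1.79 | 2.37 |
| r = 2 | 123 | 205 | 146 | 1.62 | 2.04 |
| r = 3 | 147 | 245 | 175 | 1.55 | 1.92 |
| r = 5 | 176 | 293 | 209 | 1.50 | 1.82 |
| Plan | 223 | 371 | 265 | 1.43 | 1.70 |
| Maximum m | 256 | 426 | 304 | 1.40 | 1.64 |

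(With the 45-49 base rate left unmatched, the first row is 83 cases.) About 139 of the 223 cases (223 − 84) therefore come from the multipliers. Reaching 223 needs r of about 16. Reaching 300 case knees needs 300 × 223/371 = 180 cases, so r a little above 5.

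**The case against.** Much is disclosed. Appendix B says that prevalence was analysed and that the multipliers may not carry over to true incidence. Section 8.2.4.1 says that power depends on how well enrichment works. Conservatism is called only likely, and Table 8.2 is tied to the original design assumptions, so the later overweight rule does not contradict it. Table 8.3 already uses about 300 knees rather than 371, and contralateral knees from the Progression subcohort may add cases. All of this stands. None of it tells the reader that pain sits in both definitions, which is what makes the ratio uninformative rather than merely approximate.

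Four stronger inferences are not supported.

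- A reader might infer that 223 is a ceiling, since 1/f is the limit of m. That is the limit only while prevalent cases stay in both groups. With them removed the limit gives about 256, and the base rates are a separate uncertainty.
- A reader might take r from section 4.2.2.3, which gives 5% a year with knee pain against 1-2%. That compares people with pain with all subjects, on a radiographic endpoint. It shows that pain predicts structural onset, but does not give r for this outcome and this high-risk group.
- A reader might use the ratios for pain or one factor at 50-69 (1.78 men, 1.59 women; about 146 cases) as a lower bound for the current rule. They are themselves about 1/f (614/346 = 1.77 for men; 1/0.623 = 1.61 for women), so equally uninformative. They also admit any single factor, whereas the rule adds only overweight alone.
- Table 8.5 does not rest on the multipliers; it is a generic conversion.

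One inconsistency runs the other way. Tables 5A and 8A, labelled pain or two or more factors, capture only 52 × 28.8% = 15 of 24 and 122 × 42.6% = 52 of 65 cases at the 15% weight cut-point. That is impossible if pain alone qualified there. Those tables were not used for the multipliers, but their labels or definitions need checking.

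**Conclusion.** The point holds. At ages 50-79 the multipliers equal one over the high-risk fraction because of how the terms are defined, and the 45-49 values inherit this. Table 8.1, the 265 effective knees and Table 8.2 have no demonstrated conservative margin from enrichment, and the 300 case knees behind Table 8.3 are not shown to be conservative.

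The documents do not establish the true count. Under the stated base rates, goal enrolment and the modelled high-risk fractions, it could lie anywhere from about 84 to about 256. For r of 2 to 5 it is 123 to 176, which is 21% to 45% below 223. The r values are assumptions. The calculation also assumes that the base rate applies to the disease-free stratum and that the ratio of knees to subjects stays at 371/223. The fractions omit people aged 50-69 who are eligible on overweight alone; a larger eligible fraction lowers even the maximum multiplier.

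**What to change.** - In sections 8.2.4 and 8.2.4.1, remove the description of the enrichment as conservative.
- In Appendix B, state that at ages 50-79 the multiplier equals one over the high-risk fraction because knee pain is in both definitions, and that the 45-49 values follow from the 50-59 rate.
- Do not label Table 8.1 an upper bound. Show it with a sensitivity range at goal enrolment and the stated base rates: about 84 cases (no enrichment), 123, 147 and 176 (r = 2, 3, 5, marked as assumed), and 256 (maximum).
- Use the high-risk fraction for the eligibility rule in force where it can be estimated, and carry the range into Tables 8.2 and 8.3.
- Re-set the expected case number from observed 12-month incidence before the case-control imaging sample is fixed.

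The cost is recalculation and protocol wording, with less favourable stated detectable relative risks over most of the range. Recruitment and visits are unaffected.
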